12.1 Study Treatment Administration

A listing of the individual Imprime PGG infusion data will be provided. The individual Imprime infusion data will include the date of administration, start and end time of infusion, total infusion time, actual dose (2 mg/kg or 4 mg/kg), total dose based on weight (actual dose times body weight), total dose received, total infusion volume, infusion rate (volume infused per minute), pre-medication status, details about infusion interruption (including interrupted time, restarted time, total interrupted time, and reason for infusion not restarted after interruption), any dose modifications including dose delayed/interrupted, and dose reduced, and reasons for dose modifications.

A listing of the individual pembrolizumab infusion data will be provided. The individual pembrolizumab data will include the date of administration, actual dose (200mg), actual dose received, total infusion volume, start and end time of administration, total infusion time, pre-medication status, details about infusion interruption (including interrupted time, restarted time, total interrupted time, and reason for infusion not restarted after interruption), and dose delay/interruption along with reasons.

Summary of cycles/days on study treatment and number of doses received will be provided for Imprime PGG and pembrolizumab infusion. Cycles and days on study treatment are defined as the number of cycles or days from the first dose of any study drugs until the last dose of any study drugs. As subjects may discontinue study treatment at any day of last cycle, receiving at least one dose of any study drug in the last cycle will be counted as one cycle for the calculation of cycles on study treatment.

Dose modifications including dose delayed/interrupted, dose reduced (Imprime PGG only), infusion rate reduced (Imprime PGG only) will be summarized. For each type of dose modification, the number of subjects with dose modification, total number of dose modifications and reasons for dose modifications will be summarized, in which the total number of dose modifications is calculated across all subjects with dose modifications. For example, if a subject has two dose delay/interruptions for Imprime PGG, then this subject will be counted 2 times while calculating the total number of dose delay/interruptions. For reasons of dose modifications, the total number of dose modification events will be used as denominator for the percent calculation.

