## **3. Dose Reduction**

If a subject experiences an infusion reaction despite having been administered premedication and despite the infusion time being lengthened, the PI may re-challenge the subject at the next visit by dose reducing the Imprime PGG to 2 mg/kg.

All attempts should be made to ameliorate Grade 3/4 infusion reactions by the Investigator following the 3 recommendations provided above sequentially.

In Stage 1, any Grade 3/4 infusion reactions mitigated by these actions and either resolving or decreasing to Grade 1/2, if this mitigation occurs within Cycle 1 and the Grade 3/4 infusion reaction does not recur in Cycle 2, will not be counted towards the total of > 4 or 33% of Grade 3/4 adverse events which require halting the study in Stage 1 for each individual indication. Only Cycle 1 Grade 3/4 infusion reactions (or those which recur in Cycle 2) will be counted towards the total which would halt advancement to Stage 2.

- In the event there are a total of > 4 or 33% of Grade 3/4 adverse events in Stage 1 which were unable to be ameliorated by the sequential recommendations above, the dose of Imprime PGG will be reduced to 2 mg/kg.
- Stage 1 will be repeated with an additional cohort of n=12 subjects at the reduced dose of 2 mg/kg. Toxicity at the dose of 2 mg/kg will be assessed in this additional Stage 1 cohort in the same manner as was done for the initial dose of 4 mg/kg, with the identical sequential recommendations for any observed infusion reactions.
- Advancement to Stage 2 will be halted if there are > 4 or 33% of Grade 3/4 adverse reactions. Otherwise, subjects will proceed to Stage 2 with all subjects at the new, reduced dose of 2 mg/kg.

Note that continuation onto Stage 2 requires a demonstration of at least 1 or 2 objective responses in subjects with melanoma or TNBC, respectively, in addition to meeting the adverse event requirements detailed above, at either Imprime PGG dose of 4 mg/kg or 2 mg/kg. Please refer to the [Trial Diagram](#) in [Section 2.2](#) for a schema of the study flow from start to end.

In general, any Grade 4 non-infusion or non-hematological AE will lead to the withdrawal of the subject from treatment. A dosing delay of up to 3 weeks is allowed in case of Grade 3 non-hematological AEs to reduce toxicity to baseline or Grade 0-1. Dose levels will be adjusted individually for each study drug.

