Grades 3 or 4  Grade 3: Prolonged (ie, not rapidly responsive to symptomatic medication and/or brief interruption of infusion); recurrence of symptoms following initial improvement; hospitalization indicated for other clinical sequelae (eg, renal impairment, pulmonary infiltrates)  Grade 4: Life-threatening; pressor or ventilatory support indicated	
Stop Infusion.            Additional appropriate medical therapy may include but is not limited to:
 
 
Epinephrines**
 
IV fluids
 
Antihistamines
 
NSAIDS
 
Acetaminophen
 
Narcotics
 
Oxygen
 
Pressors
 
Corticosteroids
 
 
Increase monitoring of vital signs as medically indicated until the subject is deemed medically stable in the opinion of the Investigator.            Hospitalization may be indicated.            **In cases of anaphylaxis, epinephrine should be used immediately.  Subject is permanently discontinued from further study drug treatment.
	No subsequent dosing

Appropriate resuscitation equipment should be available at the bedside and a physician readily available during the period of drug administration.

For further information, refer to the Common Terminology Criteria for Adverse Events v4.03 (CTCAE) at <http://ctep.cancer.gov>

In Stage 1, any Grade 3/4 infusion reactions mitigated by these actions and either resolving or decreasing to Grade 1/2, if this mitigation occurs within Cycle 1 and the Grade 3/4 infusion reaction does not recur in Cycle 2, will not be counted towards the total of > 4 or 33% of Grade 3/4 adverse events which require halting the study in Stage 1 for each individual indication. Only Cycle 1 Grade 3/4 infusion reactions not controlled by the above measures (or those which recur in Cycle 2) will be counted towards the total which would halt advancement to Stage 2.

Dose will be managed individually for each study drug.

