All subjects will receive Imprime PGG and pembrolizumab. Imprime PGG will be administered IV at a dose of 4 mg/kg over a 2-hour infusion time period on Day 1, Day 8, and Day 15 of each 3-week cycle for subjects at stage 1. If Stage 1 proceeds without safety concerns necessitating a second cohort at 2 mg/kg, Imprime PGG will be administered to the Stage 2 subjects at a dose of 4 mg/kg IV over a 2-hour infusion time period on Day 1, Day 8, and Day 15 of each 3-week cycle. If enrollment into an additional cohort for 2 mg/kg in Stage 1 is required and dosing proceeds to Stage 2, Imprime PGG will be administered in Stage 2 at a dose of 2 mg/kg IV over a 2-hour infusion time period on Day 1, Day 8, and Day 15 of each 3-week cycle. The pembrolizumab fixed dose of 200 mg will be administered IV over 30 minutes on Day 1 of each 3-week treatment.

Subjects will be dosed until disease progression, death, 2 years of treatment or study completion, whichever occurs first. After treatment discontinuation, subjects will be monitored every 2 months for survival until death or study completion. Study completion is defined as the death of at least 70% of subjects or 3 years after the last subject's first dose, whichever occurs earlier.

Discontinuation of treatment may be considered for subjects who have attained a confirmed CR, who have been treated for at least 24 weeks, and who had at least 2 treatments with study medications beyond the date when the initial CR was declared. Subjects who then experience radiographic disease progression may be eligible for up to 1 year of additional treatment with Imprime PGG + pembrolizumab at the discretion of the Investigator if:

- No cancer treatment was administered since the last dose of pembrolizumab
- The subject meets the safety parameters listed in the Inclusion/Exclusion criteria
- The trial is open

Subjects will resume therapy at the same dose and schedule at the time of initial discontinuation. Response or progression in this resumed course of therapy will not count towards the ORR of the primary endpoint in this trial.

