9.2.2 Duration and Elapsed Time

Durations (e.g., the duration of an adverse event, duration on study treatment, etc.) are calculated as the stop date minus the start date plus one.

For elapsed time (e.g., the time since most recent recurrence or progression), if the reference date is on or after the event date, then the elapsed time is calculated as the reference date minus the event date + 1.

When reporting OS and PFS in months, divide the number of days by 30.4375; to report in weeks divide the number of days by 7; to report in years divide the number of days by 365.25. The "year" used in these algorithms is 365.25 days long, and the "month" is one-twelfth of that year.

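### SAP 12.1 defines cycles and days on treatment by one any-drug span, which suits the regimen but not a drug stopped early, and whose days include the break before a resumed course

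*SAP*

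**What the plan says.** SAP 12.1 states: "Summary of cycles/days on study treatment and number of doses received will be provided for Imprime PGG and pembrolizumab infusion". The definition that follows is shared by both drugs. Cycles and days run "from the first dose of any study drugs until the last dose of any study drugs", and for the final cycle, "receiving at least one dose of any study drug in the last cycle will be counted as one cycle". SAP 9.2.2 says that durations, with time on study treatment as a named example, "are calculated as the stop date minus the start date plus one". Nothing is subtracted for gaps.

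Other sections expect the two drugs to part company:

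- Protocol 5.2.1.2.1 (Imprime PGG): "Dose levels will be adjusted individually for each study drug".
- Protocol 5.2.1.2.2 (pembrolizumab): "Dose will be managed individually for each study drug".
- SAP 10.1 reports treatment status, last-dose date and discontinuation reason for each drug.
- SAP 12.4 tabulates adverse events leading to withdrawal of each drug separately.

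SAP 4 and Protocol 5.8.2 let a subject stop after a confirmed complete response (CR) and come back: "Subjects who then experience radiographic disease progression may be eligible for up to 1 year of additional treatment". The resumed course is kept out of the response rate. For exposure there is no matching rule; SAP 10.1 adds only a listing of disease characteristics at re-entry.

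**The concern.** Characterising the safety of the combination is part of the primary objective, and the exposure table tells the reader how long subjects received each agent. SAP 12.2 attributes related adverse events to Imprime PGG only, pembrolizumab only or both, and SAP 10.1 reports discontinuation by drug. The only planned duration, however, is common to both drugs. If it is printed under each drug's name, the drug that stopped first is credited with time during which it was not given.

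The second issue is re-treatment. A subject who stops after CR, spends months off both drugs and then resumes has a first dose and a last dose on either side of the break. The formula counts everything between them as days on treatment.

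**Working it through.** The plan gives no exposure figure, so there is nothing to reproduce. I applied the SAP rule to the dosing schedule and compared it with drug-specific and course-specific spans. Stopping cycles and break lengths are my assumptions, because the documents give none.

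**Inputs.** Cycles last 21 days, with Imprime PGG on Days 1, 8 and 15 and pembrolizumab on Day 1 (Protocol 7.3). Days = last dose − first dose + 1 (SAP 9.2.2 and 12.1). At least 24 weeks of treatment are required before stopping after CR, and a resumed course lasts up to 1 year (SAP 4).

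**Formulas.** With first dose on Day 1, the last pembrolizumab dose in cycle c falls on Day 21(c − 1) + 1 and the last Imprime PGG dose on Day 21(c − 1) + 15. The span in days equals the study day of the last dose.

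**Both drugs run to the same cycle.** The any-drug span exceeds the pembrolizumab span by 15 − 1 = 14 days, whatever c is.

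**One drug stops early.**

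| Assumed scenario | Any-drug span | Span of the drug that stopped first | Ratio |
|---|---|---|---|
| Pembrolizumab stops after cycle 2, Imprime PGG to cycle 6 | 21×5 + 15 = 120 days, 6 cycles | 21×1 + 1 = 22 days, 2 cycles | 5.5 |
| Pembrolizumab stops after cycle 4, Imprime PGG to cycle 12 | 21×11 + 15 = 246 days, 12 cycles | 21×3 + 1 = 64 days, 4 cycles | 3.8 |
| Imprime PGG stops after cycle 4, pembrolizumab to cycle 12 | 21×11 + 1 = 232 days, 12 cycles | 21×3 + 15 = 78 days, 4 cycles | 3.0 |

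**Stop after CR, then resume.** Assume 8 cycles (24 weeks), so the last dose before the break is on Day 21×7 + 15 = 162. Dosing restarts g weeks later, on Day 162 + 7g. A resumed course of r cycles spans 21(r − 1) + 15 days: 78 days for r = 4 and 351 days for r = 17 (about 1 year). The two courses sum to 162 + 78 = 240 or 162 + 351 = 513 days. The SAP span exceeds that sum by 7g − 1 days.

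| Break | Off-drug days counted | SAP days, r = 4 (off-drug share) | SAP days, r = 17 (off-drug share) |
|---|---|---|---|
| 12 weeks | 83 | 323 (26%) | 596 (14%) |
| 26 weeks | 181 | 421 (43%) | 694 (26%) |
| 52 weeks | 363 | 603 (60%) | 876 (41%) |

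A subject who stops after 8 cycles and never resumes is shown with 162 days. The clock ends at the last dose and no off-drug time is counted.

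**Cycles.** The text does not settle whether the break adds cycles. If undosed 21-day periods are counted, the r = 4 cases would show 16, 21 and 29 cycles (323, 421 and 603 divided by 21, rounded up) against 12 actually dosed. But Protocol 7.3 ties a cycle to the frequency of pembrolizumab dosing, so months without dosing need not generate cycles.

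**The case against.** The strongest reply is that the SAP defines time on study treatment, and study treatment is the combination. An any-drug span is a conventional regimen-level measure and matches the adverse event window in SAP 12.2, which closes 30 days after the last dose of any study drug. The sentence promising the summary could mean one regimen duration plus a dose count for each drug. The table layouts are not in the available text, so this cannot be checked.

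Much of the drug-specific information is also already planned. Pembrolizumab is given once per cycle, so its dose count equals its dosed cycles. Every infusion is listed by date, and last-dose dates are listed by drug.

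Both points stand, and they limit the finding. They do not supply a planned duration for each drug, and they do not say how days are counted across a break.

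A reader might go further and infer that adverse event rates are distorted. The documents do not support that. SAP 12.2 uses counts and percentages of subjects, and no exposure-adjusted rate is planned.

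Re-entry is also likely to be uncommon. It requires a confirmed CR, at least 24 weeks of treatment, at least two treatments after CR was first declared, a decision to stop, progression, no intervening cancer therapy, safety parameters met and an open trial. Protocol 4.3.1 cites two pembrolizumab-alone TNBC cohorts, with CR rates of 0.6% and 1 in 27. Applied to 41 subjects these give 41 × 0.006 ≈ 0.25 and 41 / 27 ≈ 1.5 complete responses, before any other condition. The rate for the combination is unknown, and no melanoma rate is given.

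**Conclusion.** The point holds in a limited form. The any-drug span is acceptable as time on the regimen. It is not a valid duration for whichever drug stopped earlier: in the assumed scenarios it is about 3.0 to 5.5 times that drug's own span, against a 14-day difference for pembrolizumab when neither drug stops early. For subjects who stop after CR and resume, days on treatment include the whole break, 83 to 363 days for breaks of 12 to 52 weeks.

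Two stronger readings should be resisted. Off-drug time after CR is not counted for everyone who stops, only for those who later resume. The overcount is clear for days; for cycles the plan is silent.

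The consequence is confined to a descriptive exposure table. The response test, the adverse event percentages, the dose counts and the infusion listings are untouched. How many subjects would be affected cannot be determined from the documents. This is a low-severity point, worth correcting because the table supports a primary safety objective.

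**What to change.** In SAP 12.1:

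1. Keep the existing span as a row labelled as overall time on the regimen (any study drug).
2. Add days and cycles for Imprime PGG and for pembrolizumab, each from the first to the last dose of that drug, with the last-cycle rule applied to that drug alone.
3. For subjects who resume after CR, report the initial and resumed courses separately, exclude the off-drug interval from days, and state that it contributes no cycles.

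The cost is a few lines of SAP text and minor programming. Infusion dates for each drug are already collected and listed, so no new data or change in trial conduct is needed.

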12.2 Adverse Events

All subjects will be assessed regularly for the potential occurrence of adverse events (AEs) from the date of informed consent to 30 days after the last dose of study drug. The incidence of treatment-emergent AEs (TEAEs) will be summarized and tabulated using MedDRA (version 18.1), by System Organ Class (SOC) and Preferred Term (PT). A TEAE is defined as an AE that first occurs or worsens in severity on or after the first dose of any study drug and within 30 days after the last dose of any study drug.

The National Cancer Institute Common Terminology Criteria for Adverse Events (CTCAE) (Version 4.03) will be used to grade both clinical and laboratory AEs. A subject with several occurrences of the same AE will be counted once and classified by the most severe occurrence. AEs with missing severity ratings will be classified as having unknown severity.

An overview summary of AEs will be produced, which will include counts and percentages of subjects with any AEs and Grade III/IV AEs, AEs and Grade III/IV AEs related to study treatment, SAEs, SAEs related to study treatment, fatal SAEs, infusion reactions, AEs leading to dose delayed, dose reduced, and dose withdrawn for Imprime PGG, AEs leading to dose delayed and dose withdrawn for pembrolizumab, and AEs leading to study treatment discontinuation. AEs related to study treatment will be further categorized as AEs related to Imprime PGG and/or pembrolizumab, Imprime PGG only, pembrolizumab only, and both Imprime PGG and pembrolizumab.

A treatment-related AE is defined as an AE for which the investigator classifies the relationship to study treatment as “Yes”. A worst-case scenario approach will be taken to handle missing data, i.e. AEs related to study treatment will include events with the relationship to study treatment as ‘YES’ or missing. Adverse event data will be reviewed periodically to identify infusion reactions, new cancers, and events related to pembrolizumab overdose ($\geq 1000\text{mg}$).

The AE summary tables will use the following algorithms for counting subjects:

- **Preferred term rows:** each subject is counted once within each unique preferred term at the maximum grade. For example, if a subject has two headaches, the subject is counted only once under the preferred term “Headache”. Subjects experiencing the same AE preferred term several times with different grades will only be counted once with the maximum grade.
- **System Organ Class (SOC) rows:** each subject is counted only once at the maximum grade at each SOC level although they may have several different preferred term events within the same SOC.
- **Any event row:** each subject with at least one AE will be counted only once at the maximum grade of all AEs he/she experiences.

All AEs and study treatment related AEs will be summarized by maximum toxicity grade, SOC and preferred term. Infusion reactions will be summarized similarly. In addition, AEs will be summarized by SOC and preferred term for the following time periods: 0-3, 3-6, 6-12 and >12 months.

A summary of non-serious AEs that occurred in strictly 5% of subjects or above will be provided (no rounding for the percentage will be used in terms of 5% threshold, e.g., event with 4.9% incidence rate will not be included in this table).

The listing of all AEs and Grade III/IV will be provided. Separate listing of infusion reaction, adverse events of new cancer (that is not a condition of the study) and adverse event associated with pembrolizumab overdose as determined by clinical team review will also be provided.

Listing of AEs (if any) may be provided for the screen failure or non-treated subjects in the Screening population and the subjects in the ABA Pre-screening population.

12.3 Serious Adverse Events

Serious adverse events will be summarized similarly as AEs. A treatment related SAE is defined as an AE for which the investigator classifies the relationship to study drug as “Yes”. A worst- case scenario approach will be taken to handle missing data, i.e. SAEs related to study treatment will include events with the relationship to study treatment as ‘YES’ or missing.

For serious adverse events, the treatment-emergent time period begins at treatment enrollment through 90 days following cessation of treatment, or 30 days following cessation of treatment if the subject initiates new anticancer therapy, whichever is earlier.

Supportive listings with subject-level details will be generated for fatal and all SAEs separately.

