## 6.0 TRIAL FLOW CHART

### 6.1 Schedule of Assessments - Study Flow Chart

Cycle		C1	C2	C3	C4	C5	C6	C7 and QOC	C8 and Q4C (C12, C16, C20, C24, C28, C32)	C10 and Q4C (C14, C18, C22, C26, C30, C34)	End of Treatment (EOT)		Post-Treatment (up to 3 Years after Last Subject's 1 st Dose)	
Visit Week	Screening (-30 to -1 Days)*	W1	W4	W7	W10	W13	W16	W19 and Q6W	W22 and Q12W (W34, W46, W58, W70, W82, W94)	W28 and Q12W (W40, W52, W64, W76, W88, W100)		30-Day SFU		
Administrative Procedures														
Informed Consent	X													
Review of Entry Criteria	X													
Urine Pregnancy	X											X		
Medical Hx and Demography	X													
Enrollment	X													
Clinical Procedures / Assessments														
ECOG Status	X	X	X	X	X	X	X	X		X	X	X		
Physical Exam	X											X		
Vital Signs	X													
Weight	X	X	X	X	X	X	X	X		X	X			
AE Monitoring (Every Visit in Cycle)	X	X	X	X	X	X	X	X		X	X	X		
Administration of Pembrolizumab (D1 of Each Cycle)		X	X	X	X	X	X	X		X				
Administration of Imprime PGG (D1, D8, D15 of Each Cycle)		X	X	X	X	X	X	X		X				
Concomitant Medications (Every Visit in Cycle)		X	X	X	X	X	X	X		X	X	X		
Laboratory Procedures / Assessments														
Hematology**	X*	X	X	X	X	X	X	X		X	X	X		

10 August 2017

Confidential – Biothera Pharmaceuticals, Inc.

Cycle		C1	C2	C3	C4	C5	C6	C7 and QOC	C8 and Q4C (C12, C16, C20, C24, C28, C32)	C10 and Q4C (C14, C18, C22, C26, C30, C34)	End of Treatment (EOT)		Post-Treatment (up to 3 Years after Last Subject's 1 st Dose)	
Visit Week	Screening (-30 to -1 Days)*	W1	W4	W7	W10	W13	W16	W19 and Q6W	W22 and Q12W (W34, W46, W58, W70, W82, W94)	W28 and Q12W (W40, W52, W64, W76, W88, W100)		30-Day SFU		
CBC/Differential (Pre-Imprime infusion and 4 Hr Post-SOI of Imprime: Q4C after C2, EOT)*		X	X				X			X	X			
PBMC (Pre-Imprime infusion and EOI of Imprime: C1, C2, C6, EOT)		X	X				X				X			
RNA/DNA (Pre-Imprime infusion and EOI of Pembro: Q4C after C2, EOT)		X	X				X			X	X			
Serum Chemistry° (QOC, EOT, SFU)	X*	X		X		X		X			X	X		
Coagulation Tests	X*													
Serum ABA (Pre-Imprime Infusion and EOI of Imprime: Q4C after C6, EOT)	X (within 90 days)	X	X	X	X	X	X			X	X			
Serum Cytokines & Complement (Pre-Imprime Infusion and EOI of Imprime: Q4C after C6, EOT)		X	X	X	X	X	X			X	X			
PK (C1, C3 only)		X		X										
Urinalysis	X													
12-Lead ECG	X													
Efficacy Measurements														

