### 7.2 Screening Period

Prior to any study-specific assessments or Screening procedures, a written, signed ICF will be obtained from subjects. A copy of the signed ICF will be provided to the subject.

A Screening examination should be performed between 1 and 30 days before the first day of treatment to determine study eligibility. Subjects who meet all entry criteria will be enrolled into the study.

A Screen Failure Log must be maintained by the Investigator for all screened subjects.

A subject may be re-screened an additional 2 times if entry criteria are not met, as long as this occurs within 90 days of the signing of the ICF.

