### 7.3 Treatment Period (Treatment Cycles)

Study Day 1 is defined as the day of the first dose of study medication.

The study treatment period will be divided into treatment cycles. Each cycle will be 3 weeks in duration and defined by the frequency of pembrolizumab administration. During each cycle, subjects will dose weekly with Imprime PGG for all 3 weeks (Days 1, 8, and 15). Pembrolizumab will be dosed on D1 of each 3-week cycle. Subjects will be dosed until

disease progression or death or study termination or 2 years or until any of the criteria for study drug discontinuation are met (whichever occurs first).

See [Section 5.2.2 Timing of Dose Administration](#) for the order in which the study medications must be administered.

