#### **8.1.2 Reporting and Treating Non-serious Adverse Events**

It is the responsibility of the Investigator to perform regular assessments for AEs. Subjects will be regularly queried about the occurrence of any AEs and will be monitored throughout the study for reactions to study drug and/or study procedures. The Investigator and clinical staff will record all AEs, whether volunteered by or elicited from the subject, at anytime

during a subject's participation in the study. All events occurring prior to the first dosing will be recorded on the Medical History eCRF, except an SAE leading to exclusion from the trial or as a result of a protocol-specified intervention as described in Section 8.2.2, will be recorded on the Adverse Event eCRF. All AEs occurring at any time after the initiation of the first dose of study drug up to 30 days following the last dose of study drug will be recorded on the Adverse Event eCRF. Adverse events will be recorded according to the CTCAE v4.03 (Appendix 14.4). Adverse events meeting the definition of SAE require additional reporting as described in the following section.

All subjects experiencing an AE will be evaluated by the Investigator and monitored until resolution of the event or until the Investigator deems the event clinically stable and/or at an acceptable level. Unless the event requires hospitalization (SAE), medical treatment will be provided to the subjects at the unit, and treatment medication and/or medical procedures will preferably be provided under the guidance of the treating-Investigator's clinical discretion. All AEs, including clinically significant laboratory abnormalities, will be followed until resolution. Serious adverse events require special reporting in addition to documentation in the eCRF as described in the section on Serious Adverse Events.

It is the Investigator's responsibility to provide his/her assessment of the relationship of the event to the study drug and the severity of the event using the following scales:

- Relationship
  - No (unrelated, not related, no relation) – The time course between the administration of study drug and the occurrence or worsening of the AE rules out a causal relationship and another cause (concomitant drugs, therapies, complications, etc.) is suspected

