6 ANALYSIS POPULATIONS

The **ABA pre-screening** population will comprise all subjects who have been pre-screened for ABA test only (who have signed the ABA informed consent form but not the full informed consent form).

The **Screening** population will comprise all subjects who have been screened for the study (who have signed the full informed consent form).

The **All Treated** population will comprise all subjects in the Screening population who receive at least one dose of study treatment. The All Treated population will be the primary population for the baseline characteristics and safety analysis and the secondary population for the efficacy analysis.

The **Evaluable** population will comprise all subjects in the All Treated population who 1) have measurable disease at baseline per RECIST 1.1, AND 2) have at least one post-baseline radiological disease assessment, or discontinue study treatment as a result of progressive disease, death, or a treatment-related adverse event before the first post-baseline radiological disease assessment. The Evaluable population will be the primary population for the efficacy analysis.

The **Per-Protocol** population will comprise all subjects in the All Treated population who do not have any important protocol deviations (IPD) as defined in the study IPD list. The Per- Protocol population will be the tertiary population for the efficacy analysis.

In the Screening population, subjects who do not meet eligibility criteria will be defined as screen failures, and subjects who meet all eligibility criteria but do not receive any study treatment will be defined as non-treated subjects. The Screening population will comprise of All Treated subjects, non-treated subjects, and screen failure subjects.

Limited data will be collected for the ABA pre-screening population and the non-treated subjects and screen failure subjects in the Screening population. Summaries of these data may be produced:

- ABA Pre-screening population: ABA level at screening, demography, inclusion/exclusion, adverse event (if any), concomitant medication (if any) and death data will be collected;
- Screen failure subjects: ABA level at screening, demography, inclusion/exclusion, adverse event (if any), concomitant medication (if any) and death data will be collected;

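### SAP 12.3 opens the treatment-emergent SAE period at an undefined 'treatment enrollment' instead of first dose, so it does not match the TEAE definition in SAP 12.2

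*SAP*

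**What the plan says.** - SAP 12.2 ties treatment emergence to exposure: "A TEAE is defined as an AE that first occurs or worsens in severity on or after the first dose of any study drug", and closes the period 30 days after the last dose.
- SAP 12.3 first says "Serious adverse events will be summarized similarly as AEs", then sets a different period: "For serious adverse events, the treatment-emergent time period begins at treatment enrollment through 90 days following cessation of treatment". It shortens the end to 30 days if the subject starts new anticancer therapy.
- Protocol 8.2.2 uses the same start and end points as SAP 12.3, but as the period in which SAEs must reach the sponsor within 24 hours.
- Protocol 7.2, on the Screening Period, says: "Subjects who meet all entry criteria will be enrolled into the study". In the Protocol 6.1 flow chart, the Enrollment row has its only mark in the column headed "Screening (-30 to -1 Days".
- Protocol 7.3 puts dosing later: "Study Day 1 is defined as the day of the first dose of study medication".
- Protocol 8.1.2 sets the default record for early events: "All events occurring prior to the first dosing will be recorded on the Medical History eCRF". It makes two exceptions, which go on the Adverse Event eCRF: SAEs that lead to exclusion, and SAEs that result from a protocol-specified intervention.

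**The concern.** A treatment-emergent period should begin when exposure begins. SAP 12.3 has taken a collection rule, which properly starts early, and used it as an analysis definition. If enrollment means what the flow chart shows, a serious event in a subject who has not yet received either drug can be reported as treatment-emergent.

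Safety of the combination is a primary objective, and there is no concurrent control arm. A misattributed event therefore goes straight into the reported rate, with no comparator carrying the same error. The overview table in SAP 12.2 shows AEs and SAEs together. With two definitions in force, a subject could count as an SAE case in that table without being a TEAE case, and nothing on the page would say why.

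**Working it through.** The plan gives no figure to reproduce. The check compares definitions and then works out the effect of one event.

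**1. The two periods side by side**

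| | Start | End |
|---|---|---|
| TEAE (SAP 12.2) | First dose of any study drug | 30 days after last dose |
| Treatment-emergent SAE (SAP 12.3) | Treatment enrollment | 90 days after cessation, or 30 days if new anticancer therapy starts |

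They differ at both ends.

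**2. Where enrollment falls.** The flow chart and Protocol 7.2 put enrollment in Screening, and first dose is Study Day 1. The SAP also separates eligibility from dosing: "subjects who meet all eligibility criteria but do not receive any study treatment will be defined as non-treated subjects". On this reading the pre-dose interval admitted by SAP 12.3 runs from enrollment to first dose. Its outer limit is the 30 days from Day -30 to Day -1. The real interval is shorter, because enrollment follows confirmation of the entry criteria and the time from consent to enrollment lies outside the period. With a first-dose start the interval is 0 days.

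**3. Which pre-dose SAEs could reach a table.** Safety analyses use the All Treated population unless stated otherwise (SAP 12), so the subject must later be dosed.
- *SAE leading to exclusion:* recorded on the Adverse Event eCRF, but the subject is not dosed and is outside All Treated. Not counted.
- *SAE from another cause, such as comorbidity:* recorded as Medical History under Protocol 8.1.2. Generally not counted.
- *Event caused by progression of the cancer:* not an AE at all under Protocol 8.1.1. Not counted.
- *SAE from a protocol-specified intervention in a subject later dosed:* on the Adverse Event eCRF, in All Treated, inside the SAP 12.3 period and outside the SAP 12.2 period. Counted. A serious complication of the optional pre-dose biopsy is the obvious example.

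**4. Size per subject.** Planned totals at the dose carried forward are 12 + 17 = 29 for melanoma and 12 + 29 = 41 for TNBC.
- Melanoma: 1/29 = 3.4 percentage points.
- TNBC: 1/41 = 2.4 percentage points.

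Replaced subjects who had been dosed stay in All Treated, so the true denominators could be a little larger and these effects a little smaller. The number of such subjects cannot be computed, because the documents give neither a pre-dose SAE rate nor a typical interval from enrollment to first dose.

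**5. The other end.** A subject who starts no new anticancer therapy has an SAE period up to 90 - 30 = 60 days longer than the TEAE period. An SAE in that interval is a treatment-emergent SAE but not a TEAE, whatever *treatment enrollment* means.

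**The case against.** The strongest reply is that there may be no gap. The flow chart says enrollment and Protocol 7.2 speaks of enrollment into the study; neither uses the term *treatment enrollment*. Protocol 8.1.2 names two exceptions for events before first dosing and refers to 8.2.2 for them, and 8.2.2 ties the same exceptions to the time before treatment enrollment. Read together, the two points may be meant as one. This stands as a possible reading, but not as a settled one. Protocol 8.1.2 names the first dose explicitly when it sets the AE recording period, while 8.2.2, 8.4 and 8.5 use the other term. An undefined start for a safety period needs correcting under either reading, and the same edit does it.

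It is also fair to say that few events are exposed (step 3), and that a pre-dose SAE would be visible in the SAE listings, since study day is counted from first dose (SAP 9.2.1). A listing shows the event but does not correct the summary table.

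Several stronger readings are tempting, and the documents do not support them:
- *All pre-dose SAEs become treatment-emergent.* Those between consent and enrollment are outside the period, and Protocol 8.1.2 keeps most others off the Adverse Event eCRF.
- *An expected count can be given from a background SAE rate.* Any such rate would be assumed, and an all-cause rate would ignore the Medical History routing.
- *The Stage 1 safety decision is affected.* That rule counts subjects with Grade 3/4 adverse events in Cycle 1 and does not use the SAE period.
- *Pre-dose SAEs would often be tabulated as treatment-related.* SAP 9.1.2 does impute a missing relationship as Yes, but Protocol 8.2.2 requires the investigator's causality estimate in every SAE report, so this path is remote.

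**Conclusion.** The definition should be corrected. SAP 12.3 starts treatment emergence for SAEs at an undefined point that, by the only dated enrollment in the documents, precedes any drug. SAP 12.2 starts it at first dose. The practical effect is probably small: mainly SAEs from protocol-specified interventions in subjects later dosed, at about 3.4 points per subject in melanoma and 2.4 in TNBC.

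This rests on three conditions: that *treatment enrollment* means the enrollment marked in Screening, that sites follow the Protocol 8.1.2 recording rule, and that All Treated is close to the planned totals. If the term was meant as first dosing, the size is zero and the defect is one of wording.

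A reader might infer that moving the start would make the SAE and AE tables agree. It would not, because the different ends remain. A longer SAE period may well be deliberate, but it has to be declared.

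**What to change.** 1. In SAP 12.3, start the treatment-emergent SAE period at the first dose of any study drug, as in SAP 12.2.
2. List SAEs before first dose separately, labelled as pre-treatment, and keep them out of the treatment-emergent tables.
3. Leave the Protocol 8.2.2 window unchanged, and say in the SAP that it governs expedited reporting only.
4. Either reconcile the window ends, or state in SAP 12.3 and in a footnote to the overview and SAE tables that SAEs are counted up to 90 days after treatment and TEAEs to 30 days.

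The cost is one changed phrase, a short listing and a footnote. No new data are needed, and the change can be made before the database freeze.
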